In Phase 1 clinical trials laboratory parameters of the thyroid gland, such as thyroid-stimulating hormone, as well as liver enzymes, has been evaluated to monitor any effect in humans. No treatment-related effects were identified on thyroid hormones. Regarding liver enzymes, temporal increases up to 1.5x the upper normal value was identified following single dosing at supratherapeutic doses (600 and 800 mg) in a few individuals. Likewise, increases in ALAT was identified following repeat dosing at the 200 ng/ml dose level where 3 out of 9 subjects showed increases above the normal upper level, where one measurement at one occasion reached 3x above the normal upper level. However, 2 out of 3 placebo-treated individuals in the same cohort of subjects did also show increases above the normal upper level. All increased in liver enzymes were without concomitant changes in alkalic phosphatases, and bilirubin, and all values returned to normal at the end of the study. Nevertheless, liver values should be carefully monitored in upcoming clinical trials, and any clinically significant increases in liver enzymes should be carefully assessed and assessed relative to the subjects' pretreatment liver function and comedication.

Studies on the compound's ability to induce metabolic pathways in primary human hepatocytes have identified AP1189 as a weak inducer of CYP1A2 (also weak compared to omeprazole). Co-medication with compounds metabolized through the CYP1A2 pathway should therefore until further be avoided.

The cardiovascular study in minipigs showed an increase in relative heart rate at the highest dose tested (80 mg/kg). Consequently, even if this study did not reveal any treatment-related effects on blood pressure and ECG parameters, particular attention has been applied to the heart in Phase 1 clinical study. Dedicated tendency analysis on continued ECG assessments was conducted after both single and multiple dosing in Phase 1. The analyses that included testing of changes in ECG following dosing with a positive control knowing to induce QT prolongation showed no treatment effects of AP1189 on ECG or heart rate. Consequently, AP1189 has shown excellent cardiovascular safety.

Based on AUCs, the increase seems to be supra-proportional with an increase of 2.36 for AUC0-t and 2.17 for AUC0- ∞ when dose increased by 2. However, in the light of the small sample size (N = 3 or N = 6) this result should be interpreted with caution.

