21.1.6 Vital Signs

Vital signs will be collected for evaluation by the investigator. Reference values for the vital signs are presented in the table below. If any value is outside the reference range, the measurement will be repeated at the investigator's discretion, and the final measurement will be reported in the eCRF.

Table 4, Reference values for vital signs

Vital Sign Parameter	Range
Systolic blood pressure	90–140 mm Hg
Diastolic blood pressure	60–90 mm Hg
Heart rate (resting)	50–100 beats per minute (bpm)
Respiratory rate	12–20 breaths per minute

All vital sign values will be evaluated for clinically notable results as defined in Table 5, Any subject with a clinically notable vital sign abnormality will be immediately evaluated by qualified personnel to ensure that any required acute medical intervention or other appropriate supportive medical care is provided. All vital sign abnormalities, including clinically notable vital sign abnormalities, will be evaluated using appropriate medical

Protocol Code Number: SynAct-CS002

judgment to determine whether they represent AEs. Vital sign abnormalities that require medical intervention (beyond confirmatory vital sign collection) are to be regarded as AEs. Vital signs will be assessed at all visits.

Table 5, Criteria used to identify clinically notable vital sign abnormalities

Vital Sign Parameter	Value
Systolic blood pressure	≥ 160 mm Hg or < 90 mm Hg
Diastolic blood pressure	≥ 105 mm Hg or ≤ 50 mm Hg
Heart rate	≥ 120 bpm or < 40 bpm
Respiratory rate	< 12 breaths per minute or > 20 breaths per minute

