## Efficacy analysis

The HAQ-DI scale will be scored in accordance with Bruce and Fries, The Health Assessment Questionnaire (HAQ), *Clinical and Experimental Rheumatology*, 2005. Maska et al. summarize the scoring procedure as below (see https://onlinelibrary.wiley.com/doi/full/10.1002/acr.20620): "1) identify the highest subcategory score from each of the 8 categories. Adjust for use of aids/help by increasing the category score from 0 or 1 to a 2 if use of aids/help for that category (utilize table of companion aids/help for HAQ categories). If the category score is already a 2 or 3, no adjustment is made; 2) sum the category scores; and 3) divide the final sum by the number of categories answered to obtain the final HAQ score rounded to the nearest value evenly divisible by 0.125. Requires a minimum of 6 categories answered; if less, do not score."

The FACIT-Fatigue total subscale will be scored in accordance with http://www.ser.es/wp-content/uploads/2015/03/FACIT-F\_INDICE.pdf.

Change from baseline to week 4 (value at week 4 minus value at baseline) will be calculated for the following variables:

- CDAI
- DAS28
- HAQ-DI total score
- FACIT-Fatigue total subscale score
- number of swollen and/or tender joints (summarizing SJC and TJC)
- CXCL13
- IL-1β
- IL-6
- IL-10
- IL-6/IL-10 ratio
- TNF-α

In addition, percent change from baseline to week 4 (change from baseline as defined above divided by the baseline value) will be calculated for the following variables:

- CXCL13
- IL-1β
- IL-6
- IL-10
- IL-6/IL-10 ratio
- TNF-α

Indicators noting the following will be constructed, based on the above defined change in CDAI score from baseline to week 4:

- a 5-point decrease
- a 10-point decrease
- a 15-point decrease
- a 20-point decrease
- a 30-point decrease

Indicators noting a change in CDAI score will be constructed as follows:

- from severe (CDAI > 22) to moderate or lower (CDAI ≤ 22) at week 4 compared to baseline
- from severe (CDAI > 22) to low or remission (CDAI ≤ 10) at week 4 compared to baseline
- from severe (CDAI > 22) to remission (CDAI ≤ 2.8) at week 4 compared to baseline

Indicators noting a change in DAS28 will be constructed as follows:

- from > 3.2 to  $\leq$  3.2 at week 4 compared to baseline
- An indicator noting a change in DAS28 from high (DAS28 > 5.1) to moderate or lower (DAS28 ≤ 5.1) at week 4 compared to baseline

For the calculation of ACR response rates, indicators noting the following will be constructed:

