## 7 SAFETY AND TOLERABILITY ANALYSES

All safety parameters (vital signs, ECG, AEs/SAEs, laboratory abnormalities, etc.) will be summarized by treatment as well as for all subjects in total, by time point. Individual subject listings will also be prepared for all safety variables. Listings will include flagging of clinically notable vital sign abnormalities, as defined in protocol Table 5.

Patients with no post randomization data who cannot be contacted will not be counted in frequency tables. If included, such patients would reduce the frequency of Adverse Events.

Patients will be tabulated according to treatment received. Patients who have not received any trial medication (neither active treatment nor placebo) will not be included in frequency tables.

Variables are listed below (CRF annotation presented in parenthesis), along with a short description of how they will be presented.

For a list of proposed tables, see Appendix 4.

Study SynAct-CS002 – Statistical Analysis Plan

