## 7.6 Vital Signs

| Variable (CRF annotation)                        | How to be presented  |
|--|--|
| Vital signs measured (VSYN)                      | # patients and % /category
(2 categories: Yes/No), by visit         |
| Date of vital signs (VSDT)                       | Listing (and used to define visit)                                     |
| Time of vital signs (VSTM)                       | Listing only   |
| Systolic BP, mmHg (SBP)                          | n, mean, sd, median, min, max, by visit                                |
| Systolic BP, clinically significant (SBP_CS)     | <pre># patients and % /category (2 categories: Yes/No), by visit</pre> |
| Diastolic BP, mmHg (DBP)                         | n, mean, sd, median, min, max, by visit                                |
| Diastolic BP, clinically significant (DBP_CS)    | <pre># patients and % /category (2 categories: Yes/No), by visit</pre> |
| Heart rate, bpm (HR)                             | n, mean, sd, median, min, max, by visit                                |
| Heart rate, clinically significant (HR_CS)       | <pre># patients and % /category (2 categories: Yes/No), by visit</pre> |
| Respiratory rate, breaths/min (RR)               | n, mean, sd, median, min, max, by visit                                |
| Respiratory rate, clinically significant (RR_CS) | # patients and % /category
(2 categories: Yes/No), by visit         |

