## 7.7 Lead ECGs

| Variable (CRF annotation)     | How to be presented  |
|-------------------------------|--|
| ECG performed (EGPERF)        | # patients and % /category, by visit
(2 categories: Yes/No)   |
| ECG Date (EGDT)               | Listing only   |
| Rhythm, bpm (ECRHYT, ECRHYOT) | # patients and % /category, by visit
(7 categories: Sinus normal/Tachycardia/Atrial
fibrillation/Atrial flutter/Bradycardia/
Ventricular fibrillation/Other,
plus any specification for other) |

| RR Interval, beats/min (EGRR)  | n, mean, sd, median, min, max, by visit   |
|--|---|
| PR Interval, msecs (EGPR)  | n, mean, sd, median, min, max, by visit   |
| QRS Duration, msecs (EGQRS)  | n, mean, sd, median, min, max, by visit   |
| QT Interval, msecs (EGQT)  | n, mean, sd, median, min, max, by visit   |
| QTcF Interval, msecs (EGQTCF). Derived from
RR Interval (EGRR) and QT Interval (EGQT) if
missing, see Section 3.6. | n, mean, sd, median, min, max, by visit   |
| Overall interpretation (EGINTPRT)  | # patients and % /category, by visit
(4 categories: Normal/Abnormal, clinically
insignificant/ Abnormal, clinically significant/
Unable to Evaluate) |
| Description of abnormal findings (EGDESC)  | List of descriptions, by visit  |

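### The SAP body plans no change-from-baseline summary for vital signs or ECG intervals, and counts no protocol Table 5 notable values by arm

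*SAP*

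**What the plan says.** - **Numeric summaries.** SAP 7.6 (systolic and diastolic pressure, heart rate, respiratory rate) and SAP 7.7 (RR, PR, QRS, QT, QTcF) present each variable as "n, mean, sd, median, min, max, by visit". SAP 7 adds that safety parameters "will be summarized by treatment as well as for all subjects in total, by time point", so the arms do appear side by side.
- **Derived change.** In SAP 3.6, "Change from baseline to week 4 (value at week 4 minus value at baseline) will be calculated for the following variables" introduces a list made up of CDAI, DAS28, HAQ-DI, FACIT-Fatigue, the joint count, the cytokines and the IL-6/IL-10 ratio. It contains no vital sign and no ECG interval.
- **Notable values.** Protocol 21.1.6 states: "All vital sign values will be evaluated for clinically notable results as defined in Table 5". That table gives numeric cut-offs for systolic pressure, diastolic pressure, heart rate and respiratory rate. The SAP uses them in one place, SAP 7: "Listings will include flagging of clinically notable vital sign abnormalities, as defined in protocol Table 5".
- **Abnormalities that are tabulated.** SAP 7.6 counts subjects with a clinically significant value of each vital sign, yes or no, by visit. SAP 7.7 counts ECG rhythm (seven categories) and overall interpretation (four categories), by visit.
- **Baseline.** Protocol 20.1.2 records vital signs and a 12-lead ECG at Visit 2 (Day 0). The synopsis starts dosing on Day 1.
- **Shells.** SAP 7 refers to Appendix 4 for the list of tables. That appendix is a separate document and was not available for this review.

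**The concern.** The primary safety objective is to compare AP1189 with placebo. For a quantity measured before and during treatment, the informative summary is each subject's change, and the plan does not derive it. Three things are lost.

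1. **Spread and precision of change.** A reader can subtract the baseline mean from the week-4 mean. The SD, range and CI of the change cannot be recovered from two sets of raw summaries.
2. **The same subjects at both times.** After withdrawals, the baseline and week-4 means may describe different people.
3. **A per-subject count against an objective limit.** The clinical-significance flags are investigator judgements and are not tied to Table 5. Because they are counted per visit, a subject flagged at two visits is counted twice, so the counts cannot be added up to subjects with any post-baseline event. They also do not separate a new abnormality from one already present at baseline.

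In arms this small, a modest systematic shift could be hidden by between-subject spread, or suggested by chance imbalance at baseline.

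**Working it through.** The plan states no precision figure for these variables, so there is none to reproduce. The check has two parts.

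**A. What subtracting visit means gives**

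Protocol 15.1 plans up to 120 enrolled for at least 90 completers in the main study, so the planned allowance for loss is up to 30/120 = 25%. SAP 3.3 imputes nothing. Suppose a quarter of an arm leaves before week 4, and the leavers' baseline mean exceeds that of the completers by *d*.

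- Baseline mean over all subjects = completers' baseline mean + 0.25*d*.
- Week-4 mean minus that baseline mean = completers' mean change − 0.25*d*.

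The subtraction equals the mean change only if nobody leaves or *d* = 0. With complete data the mean is right, but the SD and CI are still unavailable.

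**B. Precision of the difference from placebo**

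Inputs from the protocol: at least 30 per group in the main study (23.2.1) and at least 15 per group in the sub-study (23.2.2). Pooling gives 30 + 15 = 45 per group.

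Assumptions, none of them in the documents: heart-rate SD 10 bpm, QTcF SD 20 ms, equal SD at both times, and baseline to week-4 correlation *r* of 0.5 to 0.8.

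Formulas for the 95% half-width:
- Raw week-4 values: t(2n−2) × SD × √(2/n)
- Simple change: raw × √(2(1−r))
- Baseline-adjusted: raw × √(1−r²)

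At n = 30: t(58) = 2.0017 and √(2/30) = 0.2582, so the raw half-width is 2.0017 × 10 × 0.2582 = 5.17 bpm for heart rate and 10.34 ms for QTcF.

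| r | Change factor | Adjusted factor | Heart rate: change / adjusted (bpm) | QTcF: change / adjusted (ms) |
|---|---|---|---|---|
| 0.5 | 1.000 | 0.866 | 5.17 / 4.48 | 10.34 / 8.95 |
| 0.7 | 0.775 | 0.714 | 4.00 / 3.69 | 8.01 / 7.38 |
| 0.8 | 0.632 | 0.600 | 3.27 / 3.10 | 6.54 / 6.20 |

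Baseline adjustment narrows the interval by 1 − 0.866 = 13% to 1 − 0.600 = 40%. These percentages depend on *r* alone, not on the assumed SDs. Simple change gives 0% at r = 0.5 and 37% at r = 0.8.

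Raw heart-rate half-width, and the chance that two arms differ at baseline by more than 0.25 SD, which is 2 × (1 − Φ(0.25/√(2/n))):

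| Analysis | n per arm | Raw half-width (bpm) | Chance of imbalance > 0.25 SD |
|---|---|---|---|
| Sub-study | 15 | 7.5 | 49% |
| Main study | 30 | 5.2 | 33% |
| Pooled | 45 | 4.2 | 24% |

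**The case against.** **The SAP meets the protocol.** Protocol 23.4 asks only for summaries by treatment and time point. The primary safety variables are AEs, SAEs and laboratory abnormalities (SAP 2.1.2), and vital-sign abnormalities that need medical intervention are to be treated as AEs (protocol 21.1.6). All of this stands. The gap is a missed use of data already collected, not a breach of the protocol.

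**A reader might infer that the arms are not compared at all.** That goes too far. Raw values, clinical-significance flags, ECG rhythm and ECG interpretation are all shown by arm and visit. What is missing is change from baseline and a count against Table 5.

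**Appendix 4 may already hold the tables.** This cannot be excluded. SAP 6.2 puts plasma concentrations in a listing only, yet the revision history adds an exposure table to Appendix 4, so the body is not a complete inventory. The revision history does not list a vital-sign or ECG change table, or a Table 5 count, among the version 2.0 additions, and SAP 3.6 derives no such variable. Neither fact settles what the shells contain.

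**A reader might infer that the protocol singles out heart rate as a live signal.** Protocol 11.3.2 does say that the minipig study "showed an increase in relative heart rate at the highest dose tested". The same paragraph then reports that ECG analyses in Phase 1, after single and multiple dosing and with a positive control, found no effect on ECG or heart rate. Section 10.1.6 still calls the repeat-dose QTcF evaluation ongoing, but neither section reports an effect. The laboratory emphasis named in protocol 15.10 is liver and thyroid.

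**A reader might infer that the omission bears on the Part 2 design.** Vital signs were an input to that choice, but SAP 3.7 records that the interim analysis was done under SAP version 1 and the decision communicated. Nothing changed now can affect it.

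**The gain comes from adjustment and rests on assumed values.** This is correct. Change scores alone may gain nothing in precision, which is why the request includes a baseline-adjusted difference.

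**Conclusion.** The point holds for the SAP body. Vital signs and ECG intervals have no change-from-baseline summary, and Table 5 notable values are flagged only in listings. The planned tables cannot supply the SD or CI of change, may compare different subjects across visits, and do not report how many subjects per arm newly meet a Table 5 limit.

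The likely gain from baseline adjustment is a 95% CI about 13% to 40% narrower, if the baseline to week-4 correlation lies between 0.5 and 0.8. In the main study, for the assumed SDs, that takes heart rate from ±5.2 bpm to between ±4.5 and ±3.1 bpm. The correlation and both SDs are assumptions.

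This is a worthwhile, inexpensive improvement to the final analysis. It does not show that the plan conflicts with the protocol or that a known cardiac signal is being overlooked. It is conditional on Appendix 4 not already containing the tables.

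**What to change.** First check the Appendix 4 shells. If the tables are not there, add the following to SAP 3.6, 7.6 and 7.7 for the final main, sub-study and pooled analyses:

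1. **Change from the Visit 2 value**, by arm and visit, for heart rate, systolic and diastolic pressure, respiratory rate, PR, QRS and QTcF, using subjects with both values. At week 4, give the baseline-adjusted (ANCOVA) difference from placebo with a 95% CI, labelled descriptive, at least for heart rate, blood pressure and QTcF. State the model: week-4 value on arm and Visit 2 value.
2. **Number and percentage of subjects per arm** with at least one post-baseline value meeting each Table 5 limit that was not met at Visit 2. Add a note that the Table 5 respiratory limits (below 12 or above 20) are simply the complement of the Table 4 reference range (12–20), so that row counts every out-of-range reading as notable.

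All the data are already collected, so no subjects or visits are added. The cost is a few more safety tables, repeated across the three analyses, and a short model statement in an otherwise descriptive plan.

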## 7.7 Lead ECGs

| Variable (CRF annotation)     | How to be presented  |
|-------------------------------|--|
| ECG performed (EGPERF)        | # patients and % /category, by visit
(2 categories: Yes/No)   |
| ECG Date (EGDT)               | Listing only   |
| Rhythm, bpm (ECRHYT, ECRHYOT) | # patients and % /category, by visit
(7 categories: Sinus normal/Tachycardia/Atrial
fibrillation/Atrial flutter/Bradycardia/
Ventricular fibrillation/Other,
plus any specification for other) |

| RR Interval, beats/min (EGRR)  | n, mean, sd, median, min, max, by visit   |
|--|---|
| PR Interval, msecs (EGPR)  | n, mean, sd, median, min, max, by visit   |
| QRS Duration, msecs (EGQRS)  | n, mean, sd, median, min, max, by visit   |
| QT Interval, msecs (EGQT)  | n, mean, sd, median, min, max, by visit   |
| QTcF Interval, msecs (EGQTCF). Derived from
RR Interval (EGRR) and QT Interval (EGQT) if
missing, see Section 3.6. | n, mean, sd, median, min, max, by visit   |
| Overall interpretation (EGINTPRT)  | # patients and % /category, by visit
(4 categories: Normal/Abnormal, clinically
insignificant/ Abnormal, clinically significant/
Unable to Evaluate) |
| Description of abnormal findings (EGDESC)  | List of descriptions, by visit  |

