21.1.7 Lead Electrocardiographic Evaluation

A twelve (12) lead ECGs will be obtained on all subjects at every visit throughout the trial. The ECG should be performed after the subject has rested quietly for at least 10 minutes.

The following ECG parameters will be obtained from the digital 12-lead ECG recordings: rhythm, heart rate (as measured by RR interval), PR interval, QRS duration, and QT interval. The corrected QT interval (QTcF) will be calculated using Fridericia's formula $(QTc=QT/\sqrt[3]{RR})^{43}$ or by using CliniCalc: (https://www.clinigate.com/clinicalc/corrected-qt-interval-qtc.php)

The investigator must evaluate all ECGs as normal/abnormal and if abnormal as clinically significant or not clinically significant. The printout of the ECG should be signed and dated. The overall evaluation (normal/abnormal) will be recorded on the eCRF, and if abnormal, the specific abnormality will be recorded too.

Each print-out must include the following information: trial number, subject's screening number, date of birth, and date and time of recording. All reference to the subject's name and/or social security number must be erased from the print-out so that only the subject's screening number is used as identification.

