#### Safety analysis

The QT interval on the ECGs is corrected from Bazett, Hodges or ECAPS to Fridericia. The laboratory values from the different sites may be reported in different units, which will be corrected to:

| Variable                     | Unit to be used
in
analyses/report | Conversion formula(s)                       | Comments   |
|------------------------------|--|---|--|
| Corrected QT Interval (QTc)  | QTc Fridericia                           | QTcF = QT/(RR 1/3 )  | The reported QT and RR
intervals will be used to
calculate QTcF. |
| HbA1c                        | mmol/mol                                 |   | mmol/L used at sites in
Moldova and Bulgaria                        |
| White blood cell             | 10E9/L                                   |   | g/dl used at some sites  |
| Neutrophils                  | 10E9/L                                   |   | g/dl used at some sites  |
| Lymphocytes                  | 10E9/L                                   |   | g/dl used at some sites  |
| Monocytes                    | 10E9/L                                   |   | g/dl used at some sites  |
| Eosinophils                  | 10E9/L                                   |   | g/dl used at some sites  |
| Basophils                    | 10E9/L                                   |   | g/dl used at some sites  |
| Hemoglobin                   | mmol /L                                  |   | g/dl used at some sites  |
| Red blood cells (RBC)        | 10E12/L                                  |   | g/dl used at some sites  |
| Thrombocytes                 | 10E9/L                                   |   | g/dl used at some sites  |
| Alanine transaminase (ALT)   | U/L                                      | $(\mu kat/L) *60 = U/L^2$                   | µkat/L used at some sites  |
| Aspartate transaminase (AST) | U/L                                      | $(\mu kat/L) *60 = U/L^2$                   | µkat/L used at some sites  |
| γ-glutamyltransferase (GGT)  | U/L                                      | $(\mu kat/L) *60 = U/L^2$                   | µkat/L used at some sites  |
| Bilirubin (total)            | μmol/L                                   |   |  |
| Bilirubin (conjugated)       | μmol/L                                   |   | µkat/L used at some sites  |

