|  | Table 11.4.1.76CXCL13, change from baselineto week 4 (pg/mL and percent change frombaseline), by ACR response   |  |
|  | Table 11.4.1.77IL-1β, change from baseline toweek 4 (pg/mL and percent change frombaseline), by ACR response  |  |
|  | Table 11.4.1.78IL-6 change from baseline toweek 4 (pg/mL and percent change frombaseline), by ACR response  |  |
|  | Table 11.4.1.79IL-10 change from baseline toweek 4 (pg/mL and percent change frombaseline), by ACR response   |  |

Page 54 of 55

|                           |   |  | Table 11.4.1.80 TNF-α, change from baseline to
week 4 (pg/mL and percent change from
baseline), by ACR response                                   |  |
|---------------------------|---|--|---|--|
| Appendix 4
p. 422      | Table 12.4.2.5
Biochemistry results    | ? -glutamyltransferase (GGT),
U/L   | $\gamma$ -glutamyltransferase (GGT), U/L  | Туро   |
| Appendix 4
p. 501      | Tables for Safety
Analysis             | Table 12.4.2.7hyroid function  | Table 12.4.2.7   Thyroid function   | Туро.  |
| Appendix 4
p. 502      | Table 12.4.2.10 Urine sample results      | Column headings:   | Urine sample  | Typos  |
| p. 002                    | sumpre results                            | Urin sample  | Clinicially significant abnormal value  |  |
|                           |   | Clincally significant abnormal value   |   |  |
| Appendix 4
p. 512      | Tables for Safety
Analysis             |  | Addition of table:
Table 12.4.2.15 MC1R Genotype   | Addition of sample in protocol v.8.0.                                  |
| Appendix 4
p. 576      | Tables for Safety
Analysis             | n = Number of patients in the
safety analysis set with non-
missing values
Std = Standard deviation | RR interval (beats/min) = heart rate
n = Number of patients in the safety analysis set with
non-missing values
Std = Standard deviation | Addition of footnote for clarity                                       |
| Appendix 4
p. 600      | Tables for
Pharmacokinetic
Analysis |  | Addition of table:
Table 11.4.4.1 Drug Exposure (Plasma
Concentrations)   | PK analyses believed not to be
performed when SAP v1.0 was written. |
| Appendix 4
p. 601      | Tables for
Pharmacokinetic
Analysis |  | Addition of table:
Table 11.4.4.2 Time from last dosing to
pharmacokinetic sample (hours)   | Timing of PK samples differ between individuals.                       |

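### SAP 3.6 and 7.7 derive QTcF from a heart rate in beats/min with no conversion to an RR interval in seconds, and they disagree on which ECGs are recalculated

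*SAP*

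**What the plan says.** **Formula.** The unit table under Safety analysis in SAP 3.6 gives QTcF = QT/RR^(1/3) with no unit for RR. Its comment column names "The reported QT and RR" intervals as the inputs. Protocol 21.1.7 gives the same cube-root formula, also without a unit: "The corrected QT interval (QTcF) will be calculated using Fridericia's formula". Both documents point to an online QTc calculator.

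**Input field.** SAP 7.7 lists the field as "RR Interval, beats/min (EGRR". A footnote added to the ECG tables in SAP v2.0, recorded in Appendix 5, explains it: "RR interval (beats/min) = heart rate". Protocol 21.1.7 agrees. Its ECG parameters are rhythm, "heart rate (as measured by RR interval"), PR, QRS and QT, with no separate RR time.

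**Which ECGs are recalculated.** SAP 3.6 is unconditional: "The QT interval on the ECGs is corrected from Bazett, Hodges or ECAPS to Fridericia". SAP 7.7 is conditional: QTcF is derived from "RR Interval (EGRR) and QT Interval (EGQT) if" the QTcF field is missing, with a reference back to 3.6.

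**The concern.** The formula and the field it uses do not fit together. Fridericia's correction takes the RR interval in seconds, and EGRR holds beats per minute. A programmer who follows 3.6 and 7.7 literally divides QT by the cube root of the heart rate. The result is not a QTcF, and it moves the wrong way: at fixed QT the true QTcF rises with heart rate, while this quantity falls.

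The scope rules also differ. A Bazett, Hodges or ECAPS value typed into EGQTCF is not missing, so 7.7 would keep it and 3.6 would replace it. The sections agree only if sites left EGQTCF blank whenever their machine used another correction, and neither section says that they did.

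At stake are the QTcF summaries (n, mean, SD, median, minimum, maximum) by treatment and visit. A kept Bazett value would look plausible in those tables.

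**Working it through.** Neither document states a numerical QTcF, so there is no figure of the plan's own to reproduce. The check is algebra on the stated rule.

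**Inputs**

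- Formula: QT/RR^(1/3) (SAP 3.6).
- RR field: EGRR, heart rate in beats/min (SAP 7.7; Appendix 5 footnote).
- Heart rates: the protocol's reference range in Table 4, "50–100 beats per minute (bpm"), plus 40 and 120 bpm, the limits in its Table 5 of notable values.
- QT: not given in the documents. I assume 400 ms for illustration and 350 to 450 ms as a range. The ratio below does not depend on it.

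**Unit step**

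- Correct: QTcF = QT/(60/HR)^(1/3)
- Unconverted: QT/HR^(1/3)
- Ratio, correct to unconverted: (HR/(60/HR))^(1/3) = (HR²/60)^(1/3)

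At 50 bpm the ratio is (2500/60)^(1/3) = 3.47. At 100 bpm it is (10000/60)^(1/3) = 5.50.

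| HR (bpm) | Correct QTcF, QT 400 ms | Unconverted | Ratio |
|---|---|---|---|
| 40 | 349.4 | 117.0 | 2.99 |
| 50 | 376.4 | 108.6 | 3.47 |
| 60 | 400.0 | 102.2 | 3.91 |
| 80 | 440.3 | 92.8 | 4.74 |
| 100 | 474.3 | 86.2 | 5.50 |
| 120 | 504.0 | 81.1 | 6.21 |

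For QT 350 to 450 ms over 50 to 100 bpm:

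- Unconverted values run from 350/100^(1/3) = 75.4 ms to 450/50^(1/3) = 122.1 ms.
- Correct values run from 350/(60/50)^(1/3) = 329.4 ms to 450/(60/100)^(1/3) = 533.5 ms.

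The two ranges do not overlap.

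**Scope step**

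Suppose a Bazett value, QT/(60/HR)^(1/2), is entered in EGQTCF and kept. With an assumed QT of 360 ms:

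| HR (bpm) | Bazett | Fridericia | Difference (ms) |
|---|---|---|---|
| 50 | 328.6 | 338.8 | -10.1 |
| 70 | 388.8 | 379.0 | +9.9 |
| 90 | 440.9 | 412.1 | +28.8 |
| 100 | 464.8 | 426.8 | +37.9 |

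The difference grows with heart rate above 60 bpm, and every value lies in a believable range.

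**The case against.** The best defence is that this is a loosely labelled field and not a wrong formula. The cube-root expression is standard, both documents name Fridericia, and a competent programmer would convert. The same SAP revision added the QTcF derivation and the footnote explaining that EGRR is heart rate, so the authors knew what the field held. Below the unit table, 3.6 promises that conversion formulas from medical sources will be used and documented in the Statistical Report. The cited calculator may accept heart rate directly, which cannot be checked here. Appendix 4 is a separate document that I have not seen and could state the step. Finally, a QTcF of 75 to 122 ms would hardly pass the checks in SAP 8.2 to 8.5.

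Most of this stands as a limit on impact. It does not supply the conversion: the general sentence gives no formula for this row, the row's own formula cell is filled in without the unit step, and 7.7 sends the reader back to 3.6.

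On scope, one can argue that a field named QTcF is effectively missing where only another correction exists, so that 3.6 governs. That is a reasonable reading, but the text does not require it, and quality control gives less protection here. The recalculation in SAP 8.4 covers efficacy parameters only, and checking listings against the database would merely confirm a Bazett value that the database already holds.

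**Conclusion.** The point holds, at minor severity. Followed literally, 3.6 and 7.7 produce a quantity that is not QTcF, too small by a factor of 3.5 to 5.5 over 50 to 100 bpm whatever the QT. The two sections also give different answers for a non-Fridericia value entered in EGQTCF.

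Both magnitudes are conditional. The first assumes unconverted substitution, which would probably be caught. The second assumes a Bazett value entered and kept, and its -10 to +38 ms holds at QT 360 ms over 50 to 100 bpm. The documents do not show that either happened, and they do not give the number of ECGs with QTcF missing. QTcF is summarised descriptively and is not part of the primary safety endpoint, and the investigator's overall ECG interpretation is a separate field.

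**What to change.** Make three edits, worded identically in SAP 3.6 and 7.7 where they apply to both:

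- **Formula:** QTcF (ms) = QT (ms) / (60/EGRR)^(1/3), where EGRR is heart rate in beats/min.
- **Label:** rename EGRR as heart rate, beats/min.
- **Scope:** adopt one rule that leaves no Bazett, Hodges or ECAPS value tabulated as QTcF. One such rule is to calculate QTcF for every ECG with both QT and heart rate, and to show the site-entered value in the listing only. Keeping site-entered Fridericia values would also work, provided the correction method behind each entry is known.

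The cost is one formula line, one label and one sentence, with matching code. No new data are needed.
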